# **Patient Global Impression of Change- Hunger**

The Patient Global Impression of Change (PGI-C) – Hunger is an anchor-based assessment used to interpret meaningful overall change of the Hunger PRO. PGI-C–Hunger endpoints consists of the number and percentage of responses for each category at weeks 12 and 24.

#### 4.12.2. Pain

## **Brief Pain Inventory – Short Form Questionnaire**

The BPI-SF measures pain and its interference with daily lives. It is a self-administered measure which consists of 9 items including:

- 1 historical pain item: "Have you had pain other than these every-day kinds of pain today?" (Yes = 1 / No = 0). The proportion of "Yes" will be used as a measure of historical pain status.
- 1 pain-location item that identifies the body area that hurts the most on a diagram.
- 4 pain-severity items, measured on a 0 to 10 scale, where 0 is "no pain" and 10 is the "pain as bad as you can imagine." The arithmetic mean for each of the 4 severity items will be used as the measure of the pain severity for the item.
- 2 pain-relief items:
  - "What treatments or medications are you receiving for your pain?"
  - "In the last 24 hours, how much relief have pain treatments or medications provided?" This question is measured on a 0% to 100% scale, where 0% is "no relief" and 100% is the "complete relief."
- 1 pain-interference item that includes 7 sub questions, where 0 is "does not interfere" and 10 is "completely interferes." The arithmetic mean of the 7 interference items will be used as a measure of pain interference.

## **Patient Global Impression of Severity- Pain**

The Patient Global Impression of Severity (PGI-S) – Pain is a self-administered PRO assessing the patient's perception of their overall severity of pain. The PGI-S–Pain is an anchor-based assessment used to interpret meaningful change of the BPI-SF. PGI-S–Pain endpoints consists of the number and percentage of responses for each category at baseline and weeks 12 and 24 as well as categorical shift responses from baseline to week 12 and 24.

#### **Patient Global Impression of Change-Pain**

The Patient Global Impression of Change (PGI-C) – Pain is a self-administered PRO assessing the patient's perception of their overall change in pain since the beginning of the study. The PGI-C–Pain is an anchor-based assessment used to interpret meaningful change of the pain via the BPI-SF. PGI-C–Pain endpoints consists of the number and percentage of responses for each category at weeks 12 and 24.

Protocol: R4461-PLD-20100

# 4.12.3. Anxiety and Depression

## **Patient Health Questionnaire-8**

The 8-item PHQ-8 is a self-administered instrument to measure depression. The PHQ-8 consists of 8 items each of which is scored 0 to 3, providing a 0 to 24 severity score. Scores of 5, 10, 15, and 20 represent cut points for mild, moderate, moderately severe, and severe depression, respectively.

If a patient scores between 10 to 14 on the PHQ-8, s/he should be referred to a mental health professional – if a referral is not deemed necessary, then the investigator must document why.

A referral is mandatory if the PHQ-8  $\geq$ 15 or is deemed necessary by the investigator.

## **Hospital Anxiety and Depression Scale Questionnaire**

The Hospital Anxiety and Depression Scale (HADS) questionnaire is an instrument for screening anxiety and depression in non-psychiatric populations; repeated administration also provides information about changes to a patient's emotional state over time (Zigmond, 1983; Herrmann, 1997). The HADS consists of 14 items, 7 each for anxiety and depression symptoms; possible scores range from 0 to 21 for each subscale. The following cut-off scores are recommended: 0 to 7 normal, 8 to 10 borderline abnormal, 11 to 21 abnormal. For this study, only the 7 anxiety questions will be scored.

## 4.12.4. Quality of Life

# Short Form - 36

The Short Form – 36 Survey (SF-36) is a 36-item self-administered PRO measure assessing health-related quality of life (HRQoL) concepts relevant across age, disease, and treatment group. The SF-36 assesses physical functioning, limitations due to physical health bodily pain, general health, vitality, social functioning, limitations due to emotional problems, and mental health. Patients answer questions assessing these concepts over the previous week using 3-, 5-, or 6-point Likert scales; scores range from 0 to 100, with higher scores indicating better health. These eight scales can be aggregated into two summary measures: Physical (PCS) and Mental (MCS) Component Summary scores. The SF-36 endpoints include change from baseline in PCS and MCS at weeks 12 and 24.

# 5. STATISTICAL METHODS

# **5.1.** Demographics and Baseline Characteristics

Demographic and baseline characteristics will be summarized twice, specifically by study treatment and overall for the study in the DBTP, and again in the SBTP by DB treatment group and overall for the study, unless otherwise noted.

DBTP summaries will be descriptively presented containing all patients in the DB SAF by treatment group and overall for the study, as well as by treatment group and overall for the study within each of the stratification factors (Cohort [A or B] and screening HbA1c  $\leq 7\%$  or  $\geq 7\%$ ]).

Protocol: R4461-PLD-20100

Continuous data will be summarized using the number of patients, mean, SD, median, minimum, and maximum for each treatment group and for each of the strata. First quartile (Q1) and third quartile (Q3) will be also provided for baseline fasting triglyceride. Categorical and ordinal data will be summarized using the number and percentage of patients in each group.

As applicable, other safety baseline data not listed in Section 4.1 will be presented collectively in the descriptive statistics summary tables containing respective post-baseline data.

SBTP summaries will be descriptively presented containing all patients in the SB SAF by DB treatment group (mibavademab, placebo) and overall for the study, unless otherwise noted. Parameters listed in Section 4.1 will be summarized in SBTP as described for the DBTP summaries.

# **5.2.** Medical History

Medical history will be descriptively summarized twice, specifically by study treatment and overall for the study in the DBTP, and again in the SBTP by DB treatment group and overall for the study, unless otherwise noted. DBTP summaries will be presented containing all patients in the DB SAF, and SBTP summaries will be presented with patients in the SB SAF.

All reported patient medical history will be presented by PT, primary SOC and HLT. The tables will be presented by SOC sorted alphabetically and in decreasing patient frequency of HLT based on the incidence in the study.

Patient disease characteristics as described in Section 4.2 will be summarized in the DB SAF.

#### 5.3. Prior and Concomitant Medications

All prior medications, dictionary coded by WHO-DD, will be descriptively summarized by study treatment and overall for the study, in the DBTP for patients in the DB SAF. Summaries will present patient counts (and percentages) for all prior medications, by decreasing frequency of the overall incidence of ATC followed by therapeutic class. In case of equal frequency across anatomic or therapeutic categories, alphabetical order will be used. Patients will be counted once in each ATC category (anatomic or therapeutic) linked to the medication but may be counted several times for the same medication.

For patients in the DB SAF, all concomitant medications during the DBTP, dictionary coded by WHO-DD, will be descriptively summarized by study treatment in the DBTP for patients in the DB SAF. Summaries will present patient counts (and percentages) for the concomitant medication groups described in Section 4.3 for all concomitant medications, by decreasing frequency of the incidence of ATC followed by therapeutic class. In case of equal frequency across anatomic or therapeutic categories, alphabetical order will be used. Patients will be counted once in each ATC category (anatomic or therapeutic) linked to the medication, hence may be counted several times for the same medication.

For the SBTP, concomitant medications will be dictionary coded by WHO-DD and will be descriptively summarized as described for the DBTP. For patient in the SB SAF, medications will be summarized by DB treatment group (ie, mibavademab, placebo) and overall for the SBTP.

Protocol: R4461-PLD-20100

## 5.4. Prohibited Medications

Listing of prohibited medications will be provided for the patients in the safety analysis set for the DBTP and respective SBTP. Prohibited medications are listed in the protocol and identified through medical review.

# 5.5. Patient Disposition

Patient disposition includes the description of patient status at major milestone decisions in the study as described in Section 4.5, as well as the patient analysis populations. Patient disposition and analysis populations will be summarized two times, specifically by study treatment group and overall (including screened patients and screen failures) for the patients in the DBTP, and again in the SBTP by DB treatment group and all patients receiving single-blind study treatment, unless otherwise noted. Exception listings will be generated for any patient treated but not randomized, randomized but not treated, and treated differently than randomized.

# **5.6.** Extent of Study Treatment Exposure and Compliance

The extent of study treatment exposure and compliance for the DBTP described in Section 4.6 will be assessed and summarized by treatment group, for patients in the DB SAF. The extent of study treatment exposure for the SBTP described in Section 4.6 will be assessed and summarized for all patients and by DB treatment group for patients in the SB SAF.

# **5.6.1.** Exposure to Investigational Product

Study treatment SC exposure in the DBTP and SBTP will be descriptively summarized for treatment duration and total number of injections as described in Section 4.6. Treatment duration and total number of injections will be summarized using the number of patients with data, mean, SD, median, minimum, and maximum. Additionally, the frequency of patients receiving study treatments at each weekly protocol scheduled visit will be summarized by number of patients (%).

For study treatment IV administration in the DBTP and SBTP, total number of infusions will be summarized using the number of patients with data, mean, SD, median, minimum, and maximum.

Additionally, mibavademab dosing SC exposure will be summarized cumulatively across the study, combining DBTP and SBTP for patients who received mibavademab in the DBTP.

## **5.6.2.** Study Treatment Compliance

The SC treatment compliance will be assessed by SC administration frequency for a treatment period (DBTP, SBTP), which is defined for each patient as the average number of days between 2 consecutive SC administrations during the treatment period: (last SC administration date – first SC administration date) / (total number of SC administrations during the treatment period - 1), for participants receiving at least 2 SC administrations during the treatment period.

Descriptive statistics of the SC administration frequency will be summarized separately for DBTP and SBTP by mean, SD, median, minimum, and maximum. Further, study treatment injection interruptions and incomplete injections with reason will be provided in a patient listing for those patients with incomplete injections.

Regeneron Pharmaceuticals, Inc.

Page 33 of 88

Protocol: R4461-PLD-20100

Important protocol deviations will be summarized. Both monitored and derived protocol deviations will be summarized for important deviation categories by count (percentage), and again by type of important deviation (patient count and percentage).

# 5.7. Analyses of Efficacy Variables

For statistics where international and conventional units do not impact the results (eg, means and least square (LS) means for percent changes from baseline, statistical testing for both percent and absolute changes from baseline, rates of patients below a threshold), derivations will be calculated and statistical models will be run using conventional units. For other statistics (eg, descriptive statistics at baseline and over time, absolute changes from baseline), derivations will be presented in both international and conventional units.

All efficacy assessment values obtained during the study (scheduled or unscheduled) can be used to provide a value for the efficacy endpoints as appropriate.

All efficacy measurements will be assigned to Efficacy Analysis Windows defined in Appendix 10.2, with the intent to provide an assessment for week 1 to 24 time points. For all visits post-baseline, the value used for the analyses at a given time point (eg, at week 12) is the value obtained within the corresponding efficacy analysis window. If multiple values exist for an analysis window, the value obtained closest to the targeted time of the window will be used as appropriate. Unless otherwise specified, the baseline value is defined as the last available measurement before the first double-blind study treatment administration. For patients randomized and not treated, the baseline value is defined as the last available value prior to the date of randomization.

Statistical analyses for the primary efficacy endpoints will be completed during the first step efficacy analysis (Section 7). Remaining descriptive efficacy analyses will be completed during the second step analyses.

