Placebo run-in period: Enrollment in a clinical trial can significantly affect a patient's diet and adherence to standard-of-care diabetes and hyperlipidemia medications, and thus impact study endpoints. In the initial study of metreleptin, as an example, the effect of study enrollment in improvement of TG was nearly as large as the effect of 1-month of metreleptin therapy (Oral, 2002). For this reason, a 4-week placebo run-in will be used so that any enrollment effect on baseline parameters occurs prior to randomization.

Stratification: A randomized and placebo-controlled study design is chosen to test the efficacy of REGN4461 and control for placebo and study effects on diet. Randomization will be stratified by HbA1c ($\leq 7.0\%$ or $\geq 7.0\%$) within each cohort to ensure that baseline HbA1c is similar between study arms, as not all FPLD patients have high HbA1c.

Treatment Periods: Two treatment periods are included to increase the number of patients who receive active study drug while blinded to treatment allocation, and to increase the power to detect within-group treatment effects and evaluate safety/tolerability. An analysis of REGN4461 treatment effects in patients in study arm 1 (placebo during TP1 and REGN4461 during TP2) is therefore included in secondary endpoints. Note that for endpoints evaluated in this manner, the values at the end of TP1 will serve as the beginning measurement for TP2.

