Baseline testing occurs in the screening period and the placebo run-in period (see Table 1). After baseline testing, patients in each cohort will be randomized 1:1 to study arm 1 (placebo in TP1 and REGN4461 in TP2) or study arm 2 (REGN4461 in TP1 and TP2), and stratified based on screening HbA1c (HbA1c \leq 7.0% or HbA1c \geq 7.0%) within each cohort.

On day 1, the first dose will be administered IV (mg/kg REGN4461 or placebo) and patients will be observed for at least 4 hours. Starting on day 8, patients will receive matched volumes of SC administered REGN4461 (mg QW) or placebo, respectively, once weekly for a total of 11 SC doses. Fasting blood draws will be taken every 2 weeks according to Table 2.

During the final 2 weeks of TP1, fasting blood draws will be performed weekly (weeks 10, 11, 12). The mean (geometric for TG and arithmetic for all other measures) of these 3 measurements will be taken as the end measure of TP1 and beginning measurement for TP2. Bioimpedance will be assessed during a mandatory in-clinic study visit (week 12). At the end of TP1, patients will undergo liver MRI and whole-body DXA.

12-week single-blind treatment period (TP2); Day 85 until week 24

On day 85 (week 12), patients will receive double-blind dosing in order to maintain blinding to study arm assignment and will then be observed for at least 4 hours:

- Study arm 1: IV loading dose of REGN4461 (mg/kg) followed by SC placebo;
- Study arm 2: placebo IV infusion followed by SC REGN4461 (mg).

Starting at week 13, REGN4461 (mg SC QW) will be administered in a single-blind manner to patients in both study arms (patient remains blinded to treatment allocation). Fasting TG and glucose measurements will occur every 2 weeks through week 20 (Table 2). During the final 2 weeks of TP2, fasting blood draws will be performed weekly (weeks 22, 23, 24). The mean (geometric for TG and arithmetic for all other measures) of these 3 measurements will be taken as the end measure of TP2. Bioimpedance will be assessed during the mandatory in-clinic visit (week 24). At week 24, patients will undergo liver MRI and whole-body DXA.

16-week off-drug safety follow-up period; Day 169 until week 40

This period will be used to monitor efficacy (glycemic, lipid parameters, daily lipodystrophy hunger patient reported outcome [PRO]), safety (hematology, chemistry, urinalysis, vital signs and AEs), PK and PD assessments as REGN4461serum concentrations decline.

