#### 1.2.4. Modifications from the Statistical Section in the Final Protocol

The content of this SAP reflects the content of the statistical section of Protocol R4461-PLD-20100 Amendment 1 with the following exceptions:

- Protocol Section 4. Endpoints: The definitions of endpoints are clarified in SAP Section 5.7 by replacing:
  - "elevated baseline fasting TG" into "screening TG"
  - "elevated baseline HbA1c" for defining subgroup into "screening HbA1c" to match HbA1c strata (screening HbA1c ≤7.0%, >7.0%)
  - "baseline leptin" for defining Cohort into "screening leptin"
- Protocol Section 11.3.2. Safety Analysis Set: Safety analysis set (SAF) is replaced with DB SAF and SB SAF as follows in SAP Section 3.2:
  - DB SAF includes all randomized patients who received any double-blind study drug.
  - SB SAF includes all the patients in the double-blind SAF who also received at least 1 study drug in the single-blind treatment period.
- Protocol Section 11.4.5.4. Treatment Compliance: Compliance % calculation is replaced with study treatment administration interval compliance in SAP Section 5.8.8.
- Protocol Section 11.4.3. Efficacy Analyses: The randomization strata per IVRS in the analysis models (eg, MMRM) are replaced with actual strata in SAP Section 5.7 to reflect the actual disease characteristic for statistical modeling.
- Protocol Section 11.4.3. Efficacy Analyses: Due to the early termination of the study and subsequent limited number of participants enrolled, only descriptive summaries

Protocol: R4461-PLD-20100

and line plots for fasting TG, HbA1c, fasting glucose, liver fat (MRI-PDFF), and Daily Lipodystrophy Hunger Questionnaire (DLHQ) over time will be provided by treatment group. Spaghetti plots for fasting TG, HbA1c, fasting glucose, liver fat (MRI-PDFF), and DLHQ will be provided for individual patient data across visits for the endpoints by treatment group if applicable.

Protocol: R4461-PLD-20100

Date: May 16, 2024

• SAP Section 7 Timing of Statistical Analyses: First Step Analysis and Second Step Analysis will not be performed.

# 1.2.5. Revision History for Statistical Analysis Plan Version 1

This is the original version of the SAP.

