# Table 5. Summary of Descriptive Statistics in Normally Distributed Secondary Endpoints based on REGN4461 Exposure

NOTE: Efficacy data for study treatment arm 1 (placebo) and arm 2 (REGN4461) will be combined by re-aligning to the first REGN4461 treatment administration, specifically study day 1 for arm 2 and week 12 for arm 1 will become REGN4461 Day 1. These descriptive statistics will be presented three times, specifically in Cohort A, Cohort B, and Cohort A+B.

Endpoints	Descriptive Statistic	
Absolute change in HbA1c from baseline to week 12	HbA1c mean changes from REGN4461     Day 1 to REGN4461 week 12 for combined DBTP-stable Arm 1 patients and Arm 2 patients will be provided along	

Regeneron Pharmaceuticals, Inc.

Page 38 of 88

Protocol: R4461-PLD-20100

• Absolute change in HbA1c from week 12 to week 24	with its corresponding 95% confidence interval.

 
Change in fasting glucose from baseline to week 12
 
Change in fasting glucose from week 12 to week 24
 
	• Fasting glucose mean changes from REGN4461 Day 1 to REGN4461 week 12 for combined Arm 1 and Arm 2 patients will be provided along with its corresponding 95% confidence interval.

 
Percent change in liver fat (MRI-PDFF) from baseline to week 12
 
Percent change in liver fat (MRI-PDFF) from week 12 to week 24
 
	• Liver fat (MRI-PDFF) mean changes from REGN4461 Day 1 to REGN4461 week 12 for combined Arm 1 and Arm 2 in patients with hepatic steatosis (baseline MRI-PDFF ≥8.5%) will be provided along with its corresponding 95% confidence interval.

Table 6. Summary of Statistics for Patients Randomized to Placebo in Normally distributed Secondary Endpoints

NOTE: These statistical estimates and descriptive statistics will be presented three times, specifically in Cohort A, Cohort B, and Cohort A+B.

Endpoints	Estimates	Comparison

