#### 6.4. Visit Windows

Visit windows will be programmatically imposed on those efficacy and safety measures repeatedly collected over the course of the study. These visit windows are derived from the number of days in study, specifically assigning day ranges to represent the study assessment schedule provided in the protocol. Data analyzed by time point (including efficacy, laboratory safety data, vital signs, and ECG) will be summarized using the analysis windows given in Appendix 10.2. These analysis windows will be applicable for all efficacy and safety analyses, and they are defined to provide more homogeneous data for time point-specific analyses. If multiple valid values of a variable exist within an analysis window, the nearest from the targeted study day will be selected for analysis, unless otherwise specified. If the difference is a tie, the value after the targeted study day will be used. If multiple valid values of a variable exist within a same day, then the first value of the day will be selected when time is available, else the scheduled visit will be selected.

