**Table 10: Analysis Windows for Body Weight** 

Visit Label	Targeted DBTP Study Day	Targeted SBTP Study Day	Analysis Window in Study Days	SBTP Analysis Window in Study Days
Screening	< Day 1	N/A	Measurement obtained prior to 1st study trt, and not defined as baseline visit	N/A
Baseline	Day 1	N/A	Measurement obtained closest to 1st study trt	N/A
Week 1	8	N/A	Day 2 to 15	N/A
Week 3	22	N/A	16 to 29	N/A
Week 5	36	N/A	30 to 39	N/A
Week 6	43	N/A	40 to 50	N/A
Week 8	57	N/A	51 to 64	N/A
Week 10	71	N/A	65 to 78	N/A
Week 12	85	N/A	82 to SB Day 1	N/A
Week 14	N/A	SB Day 15	N/A	SB Day 2 to 22
Week 16	N/A	29	N/A	23 to 36
Week 18	N/A	43	N/A	37 to 50
Week 20	N/A	57	N/A	51 to 64
Week 22	N/A	71	N/A	65 to 78
Week 24	N/A	85	N/A	79 to 92
FU- W5	Last study trt admin day + 35 days	Last study trt	Last study trt admin day +15 days TO last study trt admin day + 49 days	
FU-W9	Last study trt admin day + 63 days	Last study trt admin day + 50 days TO last study trt admin day + 77 days		
FU-W13	Last study trt admin day + 91 days	Last study trt admin day + 78 days TO last study trt admin day + 105 days		
FU-W17	Last study trt admin day + 119 days	Last study trt admin day + 106 days TO last study trt admin day + 126 days		

Table 11: Efficacy Analysis Windows for Fasting Triglycerides and Fasting Glucose

Visit Label	Targeted DBTP Study Day	Targeted SBTP Study Day	Analysis Window in Study Days	SBTP Analysis Window in Study Days
Screenin g	< Day 1	N/A	Measurement obtained prior to 1st study trt, and not defined as baseline visit	N/A
Baseline	Day 1	N/A	Measurement obtained closest to 1st study trt while remaining prior to 1st study trt admin	N/A
Week 2	15	N/A	Day 2 to 22	N/A
Week 4	29	N/A	23 to 36	N/A
Week 6	43	N/A	37 to 50	N/A
Week 8	57	N/A	51 to 64	N/A
Week 10	71	N/A	65 to 74	N/A
Week 11	78	N/A	75 to 81	N/A
Week 12	85	N/A	82 to SB Day 1	N/A
Week 14	N/A	SB Day 15	N/A	SB Day 2 to 22
Week 16	N/A	29	N/A	23 to 36
Week 18	N/A	43	N/A	37 to 50
Week 20	N/A	57	N/A	51 to 64
Week 22	N/A	71	N/A	65 to 74
Week 23	N/A	78	N/A	75 to 81
Week 24	N/A	85	N/A	82 to 92
FU- W5	Last study trt admin day + 35 days		Last study trt admin day +15 days TO last study trt admir day + 49 days	
FU- W9	Last study trt admin day + 63 days		Last study trt admin day + 50 d day + 77	
FU- W13	Last study trt admin day + 91 days		Last study trt admin day + 78 d day + 105	
FU- W17	Last study trt admin day + 119 days		Last study trt admin day + 106 days TO last study trt admin day + 126 days	

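### Protocol 6.1 takes the end-of-period fasting TG and glucose value as the mean of three weekly draws; the SAP uses the single week-12 or week-24 draw and does not declare the change

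*SAP*

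**What the plan says.** **Protocol.** Section 6.1 moves fasting draws from every two weeks to weekly at the end of each treatment period. Of the week 10, 11 and 12 draws it says: "The mean (geometric for TG and arithmetic for all other measures) of these 3 measurements will be taken as the end measure of TP1". The same sentence makes that mean the starting value for TP2, and a parallel sentence applies the rule to weeks 22, 23 and 24 for the end of TP2. Section 3.2.1 repeats that "the values at the end of TP1 will serve as the beginning measurement for TP2".

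**SAP.** Section 5.7 says that the "value used for the analyses at a given time point (eg, at week 12) is the value obtained within the corresponding efficacy analysis window". Section 6.4 adds: "If multiple valid values of a variable exist within an analysis window, the nearest from the targeted study day will be selected for analysis". In Appendix 10.2, Table 11 gives fasting TG and fasting glucose separate windows: days 65-74 (week 10), 75-81 (week 11) and 82 to SB Day 1 (week 12), then SB days 65-74, 75-81 and 82-92 for weeks 22, 23 and 24. The TG model in 5.7.1.1 enters weeks 10, 11 and 12 as separate time points and reports the LS mean at week 12. For the pooled first-exposure summaries, Table 5 re-aligns the data: "specifically study day 1 for arm 2 and week 12 for arm 1 will become REGN4461 Day 1". No SAP section forms a three-draw mean.

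**Declared changes.** SAP 1.2.4 opens: "The content of this SAP reflects the content of the statistical section of Protocol R4461-PLD-20100 Amendment 1 with the following exceptions". The averaging rule is not in the list that follows. That list does limit efficacy output to descriptive summaries and plots because of early termination.

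**The concern.** The two documents define the end-of-period value differently. Under protocol 6.1 it combines three draws; under the SAP it is one. A reader who derives week 12 from the protocol and a programmer who follows the SAP can report different percent changes for the same patient.

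Protocol 3.2.1 states that fasting TG varies from day to day within patients and that averaging several readings improves the baseline estimate. The same reasoning would favour averaging at the end of a period. With very few patients, one noisy draw can move a group median noticeably.

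At stake are the week-12 and week-24 TG and glucose summaries. If they are still produced, the TG part of the stability flag (SAP 5.7.2) and the Arm 1 starting value for TP2 are affected too.

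The scope is narrow. HbA1c has no week-11 or week-23 draw, liver fat has one scan at each of weeks 12 and 24, and the last-value baseline is protocol 11.4's own rule.

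**Working it through.** **1. Reproduce the plan's figure.** Inputs from protocol 11.2: SD of log TG 0.87, 10 per arm, 90% CI. Half-width = t(0.95, 18) × 0.87 × √(2/10) = 1.734 × 0.87 × 0.447 = 0.675 (stated 0.67). The same formula gives 1.404, 1.594 and 1.724 for HbA1c at 10, 8 and 7 per arm (stated 1.4, 1.59 and 1.72).

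**2. Two rules, one patient (invented values, baseline 400 mg/dL).**

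| Draws at weeks 10, 11, 12 | Protocol 6.1: geometric mean | SAP: week 12 only |
|---|---|---|
| 200, 260, 420 | 279.5 (-30.1%) | 420 (+5.0%) |
| 300, 280, 220 | 264.4 (-33.9%) | 220 (-45.0%) |

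**3. Assumptions for size.** The documents give no within-patient SD of log TG (s), so take 0.25, 0.40 and 0.50. Read 0.87 as the SD of the log change to a single end draw. Let f be the variance of the three-draw mean divided by s²:
- independent draws: f = 1/3
- weekly AR(1) correlation 0.5: f = (3 + 2 × (0.5 + 0.5 + 0.25))/9 = 0.611

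**4. Draw noise in a patient's change from a single-draw baseline.** The ratio of mean to single is √((1 + f)/2) = 0.816 or 0.898, a cut of 18% or 10%. For a truly unchanged patient at s = 0.40 with independent draws, the 95% noise range is:
- single draw: exp(±1.96 × 0.40 × √2) - 1, which is -67% to +203%
- three-draw mean: exp(±1.96 × 0.40 × √(4/3)) - 1, which is -60% to +147%

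**5. CI half-width.** The SD of the change becomes √(0.87² - s²(1 - f)).

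| s | Independent draws | AR(1) 0.5 |
|---|---|---|
| 0.25 | 0.656 (3% narrower) | 1.6% narrower |
| 0.40 | 0.625 (7%) | 4.2% |
| 0.50 | 0.596 (12%) | 6.6% |

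**6. Arm 1 contrast.** (W24 - W12) - (W12 - baseline) = W24 - 2·W12 + baseline. The noise ratio is √((f + 4f + 1)/6) = 0.667 or 0.822, a cut of 33% or 18%. The week-12 value enters twice, so its noise weighs most here.

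**7. TG stability flag.** For a truly stable patient, the probability of a change of at most +25% is Φ(ln 1.25/(s√2)) on single draws and Φ(ln 1.25/(s√(4/3))) with the end mean. For s = 0.25, 0.40 and 0.50 this is 0.74, 0.65 and 0.62 against 0.78, 0.69 and 0.65 (independent draws).

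**8. Does the MMRM recover the mean?** No. The SAP's TG model crosses treatment, strata and baseline with time point, so every visit has the same regressors. With complete data the week-12 contrast then equals an ANCOVA on week-12 values alone. A simulated complete dataset with unstructured covariance gave 0.4036 both ways. Weeks 10 and 11 contribute only where data are missing.

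**The case against.** The strongest reply is that the conflict starts inside the protocol. Its endpoints refer to week 12, and 11.4.3.1 specifies an MMRM with week as a factor and no averaging. The SAP follows those sections, and its change list is framed around the protocol's statistical section, whereas averaging sits under study design. This stands as an account of how the gap arose, but it does not close it. The 6.1 rule is explicit, and the SAP list already reaches beyond Section 11 to the endpoints in Section 4.

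Second, protocol 3.2.1's statement about TG variability concerns the screening and baseline period, and 6.1 gives no reason for the weekly end draws. Carrying the rationale over is an inference. That is correct, but the mismatch does not depend on it.

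Third, output is now descriptive, so the CI and Arm 1 contrast figures describe analyses no longer planned, and the SD is assumed. Also, 0.87 might already describe a three-draw endpoint. In that case 0.675 is the averaged figure, and at s = 0.40 a single draw would give 1.734 × √(0.87² + 0.16 × 2/3) × 0.447 = 0.72. These points limit the size; they do not remove the difference in the retained summaries.

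Finally, Table 5 covers glucose but not TG; for TG, Table 7 uses the same re-aligned time labels without defining the start value. All draws are kept and shown by visit, so the three-draw mean can still be derived.

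**Conclusion.** The point holds. For fasting TG and fasting glucose, the SAP replaces an explicit protocol rule with a single draw and does not say so. Protocol 6.1 and 11.4.3.1 also need to be reconciled with each other.

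The effect is extra noise, with no bias between arms claimed. The gain from the three-draw mean is modest for group precision and larger for individual patients and for any contrast that uses week 12 as both an end and a start value. All sizes rest on the assumed within-patient SD, on the reading of 0.87, and on the correlation between weekly draws. The textual conflict rests on none of these. Because reporting is now descriptive in a very small sample, the practical effect is on the week-12 and week-24 TG and glucose summaries. It should be fixed.

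**What to change.** In SAP 5.7, 6.4 and Table 11, define the end-of-TP1/start-of-TP2 and end-of-TP2 values as the geometric mean (fasting TG) or arithmetic mean (fasting glucose) of the fasted draws in the week 10-12 and week 22-24 windows. Then:

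- Add a missing-draw rule, for example: average two or three draws, use and flag a single draw, otherwise set to missing.
- Keep the by-visit summaries and plots.
- If the MMRM is run, report the treatment contrast averaged equally over weeks 10, 11 and 12. On the log scale this matches the geometric mean.
- State whether HbA1c uses week 12 and week 24 alone, or the mean of weeks 10 and 12 (22 and 24).

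If the single draw is intended, list it in SAP 1.2.4 as a departure from protocol 6.1 and justify it.

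The cost is SAP wording and programming, since every draw is already scheduled. The drawback is that the value then reflects the last two weeks of the period rather than one day, so it lags slightly if TG is still changing.
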